	All patients (N=...)		Monitoring (N=...)		Surveillance (N=...)		P
Percutaneous thrombectomy	%	N	%	N	%	N	...
Technical success ^a	%	N	%	N	%	N	...
Clinical success ^b	%	N	%	N	%	N	...
Recurrent thrombosis in 3 months	%	N	%	N	%	N	...
Open thrombectomy	%	N	%	N	%	N	...
Technical success ^a	%	N	%	N	%	N	...
Clinical success ^b	%	N	%	N	%	N	...
Recurrent thrombosis in 3 months	%	N	%	N	%	N	...
No thrombectomy	%	N	%	N	%	N	...
Vascular access loss in 30 days	%	N	%	N	%	N	...
Permanent central venous catheter	%	N	%	N	%	N	...
Temporary central venous catheter	%	N	%	N	%	N	...

^a Return of thrill and bruit

^b Successful hemodialysis with the vascular access after thrombectomy: cannulated with 2 needles with prescribed dialysis blood flow

Statistical analysis: Chi squared tests

Figure 7D: Kaplan-Meier curves of (A) primary patency (any access-related intervention), (B)

assisted primary patency, and (C) secondary patency after interventions for thrombosis

Include interventions that result in clinical success. Censoring after loss of primary patency. Statistical comparison between monitoring and surveillance groups with log-rank tests.

Table 8A: Duplex ultrasound core lab assessment^a

	All lesions ^b (N=...)	Intimal hyperplasia type (N=...)	Shrinking type (N=...)	No stenosis type (N=...)
Inner diameter stenosis (mm)	... + SD	... + SD	... + SD	... + SD
Outer diameter stenosis (mm)	... + SD	... + SD	... + SD	... + SD
Inner diameter reference vessel (mm)	... + SD	... + SD	... + SD	... + SD
Outer diameter reference vessel (mm)	... + SD	... + SD	... + SD	... + SD
Intimal hyperplasia rate (%)	... + SD	... + SD	... + SD	... + SD
Vascular constriction rate (%)	... + SD	... + SD	... + SD	... + SD
Stenosis rate (%)	... + SD	... + SD	... + SD	... + SD

^a For multiple stenosis, the most severe stenosis (i.e. highest PSV-ratio) is chosen.

^b Definitions according to Suemitsu et al. J Endovasc Ther 2025;32(5):1607-1613. No stenosis is defined as <50% stenosis rate and >2 mm inner diameter.

Table 8B: Duplex ultrasound findings (selection of duplex ultrasound assessments with available images of the stenosis and subsequent balloon angioplasty of the stenosis)

	Intimal hyperplasia type (N=...)		Shrinking type (N=...)		No stenosis type (N=...)		P
Access flow (mL/min)	... + SD	N	... + SD	N	... + SD	N	...
Diameter outflow vein (mm) ^b	... + SD	N	... + SD	N	... + SD	N	...
Stenosis		N		N		N	...
None	%	N	%	N	%	N	
Single	%	N	%	N	%	N	
Multiple	%	N	%	N	%	N	

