Stent	%	N	%	N	%	N	...
Covera	%	N	%	N	%	N	
Viabahn	%	N	%	N	%	N	
Wrapsody	%	N	%	N	%	N	
Supera	%	N	%	N	%	N	
Stent diameter (mm)	... + SD	N	... + SD	N	... + SD	N	...
Stent length (mm)	... + SD	N	... + SD	N	... + SD	N	...
Treatment effect							
Subjective assessment							
Luminal loss before treatment (%)	... + SD	N	... + SD	N	... + SD	N	...
Luminal loss after treatment (%)	... + SD	N	... + SD	N	... + SD	N	...
Core lab assessment							
Luminal loss before treatment (%)	... + SD	N	... + SD	N	... + SD	N	...
Luminal loss after treatment (%)	... + SD	N	... + SD	N	... + SD	N	...

^a Clinical indicators of flow dysfunction refer to the decision rules for interventions defined in the study protocol (and used to send notifications to the study sites).

^b Outflow vein may be subdivided into cannulation zone / outflow vein / cephalic arch / swing segment when angiography images are available.

Data are presented as proportions or as mean with standard deviation.

Statistical analysis: One-way ANOVA for continuous variables and Chi squared test for categorical variables.

Figure 8D: Kaplan-Meier curves for (A) primary patency (target lesion), (B) assisted primary patency, and (C) secondary patency after percutaneous balloon angioplasty for 3 stenosis types
 Statistical analysis: log rank test

Table 8E: Association between duplex ultrasound stenosis type and target lesion primary patency after balloon angioplasty

	Target lesion primary patency ^a	
	HR (95% CI)	P
Stenosis type		...
No stenosis	Reference	
Intimal hyperplasia	... (....-....)	
Shrinking	... (....-....)	
Sex (male)	... (....-....)	...
Age (/year)	... (....-....)	...
Diabetes mellitus (yes)	... (....-....)	...
Smoking history (current vs stopped/never)	... (....-....)	...
Use of antithrombotics		...
No	Reference	
Antiplatelet therapy	... (....-....)	
Anticoagulant therapy	... (....-....)	
Fish oil supplements (yes)	... (....-....)	...
Vascular access type (graft vs fistula)	... (....-....)	...
Baseline access flow (/mL/min)	... (....-....)	...
Previous vascular access interventions (yes)	... (....-....)	...
Study group after treatment (surveillance)	... (....-....)	...
Stenosis (multiple vs single)	... (....-....)	...
Indication for intervention		...
Clinical indicators of flow dysfunction ^a	Reference	
Access flow <500 mL/min without clinical indicators of flow dysfunction ^a	... (....-....)	
Vascular access thrombosis	... (....-....)	
Balloon diameter (/mm)	... (....-....)	...

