Balloon inflation time (/min)	... (....-....)	...
Balloon inflation pressure (/atm)	... (....-....)	...
Paclitaxel-coated balloon (yes)	... (....-....)	...
Covered stent (yes)	... (....-....)	...
Luminal loss before treatment (/%)	... (....-....)	...
Luminal loss after treatment (/%)	... (....-....)	...

^a For multiple stenosis, the target lesion is the most severe stenosis (i.e. highest PSV-ratio with duplex ultrasound).

Statistical analysis: all variables will be entered into multivariable Cox regression models

Check for assumptions of statistical model: linearity, multicollinearity, independence of errors, and proportional hazards

Table 8F: Complications of percutaneous interventions

	Intimal hyperplasia type (N=...)		Shrinking type (N=...)		No stenosis type (N=...)		P
No complications	%	N	%	N	%	N	...
Extravasation after angioplasty	%	N	%	N	%	N	...
Balloon dilation	%	N	%	N	%	N	...
Covered stent	%	N	%	N	%	N	...
Other treatment	%	N	%	N	%	N	...
Bleeding from access site	%	N	%	N	%	N	...
Compression dressing	%	N	%	N	%	N	...
Thrombin injection	%	N	%	N	%	N	...
Surgical closure	%	N	%	N	%	N	...
Other treatment	%	N	%	N	%	N	...
Other complication	%	N	%	N	%	N	...

Statistical analysis: Chi squared tests

Table 9A: Cannulation practice – comparison between study groups

		All patients (... dialysis sessions)		Monitoring (... dialysis sessions)		Surveillance (... dialysis sessions)	P
Cannulation technique		N		N		N	...
Rope ladder	%	N	%	N	%	N	
Buttonhole	%	N	%	N	%	N	
Ultrasound-guided cannulation		N		N		N	...
No	%	N	%	N	%	N	
Cannulation site determination	%	N	%	N	%	N	
Ultrasound-guided puncture	%	N	%	N	%	N	
Needle position assessment	%	N	%	N	%	N	
Needle type		N		N		N	...
Steel	%	N	%	N	%	N	
Plastic	%	N	%	N	%	N	
Needle size		N		N		N	...
15G	%	N	%	N	%	N	
16G	%	N	%	N	%	N	
17G	%	N	%	N	%	N	
Other	%	N	%	N	%	N	
Single needle prescription	%	N	%	N	%	N	...
Cannulation difficulties ^a	%	N	%	N	%	N	...
Cannulation failure ^b	%	N	%	N	%	N	...
Arterial punctures		N		N		N	...
1	%	N	%	N	%	N	
2	%	N	%	N	%	N	
3 or more	%	N	%	N	%	N	
Venous punctures		N		N		N	...
1	%	N	%	N	%	N	
2	%	N	%	N	%	N	
3 or more	%	N	%	N	%	N	
Hematomas	%	N	%	N	%	N	...

^a> 1 attempt to place and secure two needles (or one needle for dialysis sessions with single needle prescription)

^binability to place and secure two needles (or one needle for dialysis sessions with single needle prescription)

Statistical analysis: Chi square tests

Table 9B: Cannulation practice – predictors of cannulation problems

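### Table 8E's only hazard ratio for stenosis type is conditional on the procedure and its result, and the SAP neither says so nor plans an adjusted overall estimate

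*SAP*

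**What the plan says.** SAP section 6, Table 8E, is titled "Association between duplex ultrasound stenosis type and target lesion primary patency after balloon angioplasty". The method line below it states that "all variables will be entered into multivariable Cox regression models". No reduced or staged model is described.

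Besides patient, access and indication variables, the rows list balloon diameter, inflation time, inflation pressure, paclitaxel-coated balloon, covered stent, luminal loss before treatment and "Luminal loss after treatment".

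The time order is given in the title of Table 8B, which describes its data as a "selection of duplex ultrasound assessments with available images of the stenosis and subsequent balloon angioplasty of the stenosis". The reference category for type is defined in a footnote to Table 8A: "No stenosis is defined as <50% stenosis rate and >2 mm inner diameter".

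Two other displays bear on the question. Figure 8D gives Kaplan-Meier curves by stenosis type with a log rank test. Table 8C compares the procedural variables and luminal loss across the three types, with P values.

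**The concern.** Stenosis type is read on a duplex made before treatment. A reader of Table 8E will take its hazard ratio as the answer to whether type predicts loss of patency after angioplasty, allowing for differences between patients. The planned model answers a narrower question: whether type still predicts loss of patency among lesions treated in the same way and left with the same residual narrowing.

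The two answers agree only if type has no bearing on how the procedure is done or on what it achieves. If one type recoils more and therefore leaves more residual narrowing, the residual narrowing carries part of that type's association with patency, and adjusting for it removes that part. Neither the title nor the footnotes tell the reader which association is reported, and no adjusted hazard ratio for the overall association is planned.

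**Working it through.** The SAP gives no event count, power or expected hazard ratio for Table 8E, so there is no figure to reproduce. The check has three steps.

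**1. Sort the model terms by timing.** Counting degrees of freedom from the rows of Table 8E:

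- Stenosis type: 2.
- Patient, access, indication and study-group terms: sex 1, age 1, diabetes 1, smoking 1, antithrombotics 2, fish oil 1, access type 1, baseline flow 1, previous interventions 1, study group after treatment 1, multiple stenosis 1, indication 2. Sum 14.
- Luminal loss before treatment: 1.
- Recorded at or after the angioplasty: balloon diameter, inflation time, inflation pressure, paclitaxel-coated balloon, covered stent, luminal loss after treatment. Sum 6.

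Total 2 + 14 + 1 + 6 = 23, so 6 of the 21 covariate terms belong to the procedure or its result. Study group after treatment is not part of this criticism: Table 2L shows a randomization following successful interventions, so it is not a consequence of type.

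**2. See how the SAP treats these six elsewhere.**

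- Luminal loss after treatment stands under *Treatment effect* in Table 8C. Residual stenosis below 30% is the SAP's definition of technical success (section 5.1.2, item 6, and Table 7A). A quantity closely related to an outcome is thus used as a covariate.
- Table 8C tests whether the six differ by stenosis type; Table 8E then holds them fixed.
- Table 8F lists a covered stent among the treatments for extravasation after angioplasty, so at least some covered stents respond to an event during the procedure.

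**3. Illustrate what conditioning can do.** All values here are assumed; none comes from the SAP. X is a two-level type contrast. Residual loss in units of 10% is R = 2 + a·X + N(0,1). Covered stent S has probability 0.15 + s·X. The log hazard is d·X + b·(R − 2) + g·S, with exponential times censored at 1.5 and n = 6,000 per scenario. Cox models were fitted with X alone and with X, R and S.

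| d | a | b | s | g | HR, X alone | HR, with R and S |
|---|---|---|---|---|---|---|
| 0.3 | 0.5 | 0.3 | 0 | 0 | 1.54 | 1.34 |
| 0.3 | 1.0 | 0.3 | 0 | 0 | 1.80 | 1.39 |
| 0.3 | 1.0 | 0.4 | 0.2 | −0.5 | 1.66 | 1.29 |
| 0 | 1.0 | 0.4 | 0 | 0 | 1.39 | 0.99 |
| 0.3 | 0 | 0.3 | 0 | 0 | 1.33 | 1.35 |
| 0.3 | 0 | 0.3 | 0.2 | −0.7 | 1.15 | 1.38 |

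With d = 0.3 the conditional hazard ratio should be exp(0.3) = 1.35. The fitted values of 1.29 to 1.39 show the simulation error. Where type acts only through residual loss (row 4), the full model reports no association. Where type acts on patency directly and also through greater use of a protective stent (row 6), the full model reports a larger one. Where type affects neither variable (row 5), the two models agree apart from simulation error and the slight non-collapsibility of the hazard ratio.

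**The case against.** The strongest reply is that a conditional hazard ratio is also an association. The SAP does not claim to estimate a total effect, and whether type adds prognostic information once the result is known is a fair question. This stands. The fault is that the plan does not say which association is meant and supplies an adjusted estimate of only one.

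A second reply is that Figure 8D and Table 8C already show the crude comparison and any differences in treatment. That softens the risk that an association would go unnoticed. But Figure 8D has no hazard ratio and no adjustment for confounders, and Table 8C is descriptive.

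Several stronger readings are tempting, and the document does not support them:

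- *That treatment choices follow from stenosis type.* Only the time order is documented. Table 8A describes the type as a core-lab reading, and nothing says that operators had it. If balloon and stent choice reflect site practice or lesion location, they are ordinary prognostic covariates. Luminal loss after treatment is the clear case of a procedural result.
- *That the hazard ratio is pulled towards 1.* If half or three quarters of a log hazard ratio of ln 2 ran through these variables, 2.0 would become exp(0.5·ln 2) = 1.41 or exp(0.25·ln 2) = 1.19. Those shares are invented, and the last simulated row moves the other way.
- *That 23 parameters overfit the model.* The SAP gives no event count for this subset, so this cannot be shown.
- *That luminal loss before treatment is the same measurement as the one defining the reference group.* The definition uses duplex stenosis rate and inner diameter, whereas luminal loss appears among the angioplasty assessments in Table 8C. The two are related in content but not shown to be identical. The planned multicollinearity check may flag an overlap, but no action is attached to it.

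**Conclusion.** The point holds as a minor one. As written, Table 8E reports a hazard ratio for stenosis type that is conditional on the procedure and its result, under a title that does not say so, and no confounder-adjusted overall estimate is planned. Luminal loss after treatment is the clearest problem; for the five procedural variables the point depends on whether type influences them. The difference between the two hazard ratios is nil if type affects none of the six variables. Otherwise it is of unknown sign and size, and the simulated figures show only that both directions are possible. Stenosis type is not among the outcomes in section 5.1.2, so the consequence is confined to this exploratory table.

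**What to change.** Make the main Table 8E model adjust only for factors fixed before the angioplasty: patient factors, access type, baseline access flow, previous interventions, indication, and single or multiple stenosis. State whether study group after treatment is kept; the point does not depend on it.

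Show the main model with and without luminal loss before treatment. That variable precedes the procedure, but the reference category is itself defined by stenosis rate and inner diameter, so it may absorb part of the contrast with the other types.

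Show the full model, with the procedural variables and luminal loss after treatment, second, labelled as conditional on procedure and result.

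The cost is one or two extra models and the matching columns. Fixing the order before the analysis also avoids choosing between the models after the results are seen.

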2.7. Timing of outcome assessments

Physical examination of the vascular access will be done at each dialysis session. Volume measurements by ultrasound dilution will be done every month. Duplex ultrasound examination of the vascular access will take place in case of flow dysfunction, and interventions for flow dysfunction are part of standard clinical care for hemodialysis patients. Subjects enrolled in the trial will be asked to fill out questionnaires (SF-VAQ, EQ-5D-5L, MCQ and PCQ) at baseline and every 3 months until 24 months of follow up.

3. Statistical Principles

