Monitoring reports ^a person-years person-years
Flow measurements person-years person-years

Table 2G: Vascular access dysfunction detected by monitoring and surveillance - Monitoring reports

	Monitoring (... reports)	Surveillance (... reports)	P
Clinical indicators of flow dysfunction	%	%	...
Physical examination	%	%	...
Weak or discontinuous thrill	%	%	...
High pitched or discontinuous bruit	%	%	...
Hyperpulsatile vascular access	%	%	...
Weak vascular access	%	%	...
No thrill or bruit	%	%	...
Recurrent problems during dialysis	%	%	...
Inability to achieve target blood flow	%	%	...
New cannulation problems	%	%	...
Prolonged bleeding	%	%	...
Unexplained fall in dialysis efficiency	%	%	...
Other findings at inspection			
Aneurysm	%	%	...
Hand ischemia	%	%	...
Infection	%	%	...
Edema	%	%	...
Skin lesions	%	%	...
Hematoma	%	%	...

Statistical analysis: Chi squared tests.

Table 2H: Vascular access dysfunction detected by monitoring and surveillance - Surveillance flow measurements

	Monitoring (... measurements)	Surveillance (... measurements)	P
Access flow <500 mL/min ^b	%	%	...
With clinical indicators of flow dysfunction	%	%	...
Without clinical indicators of flow dysfunction	%	%	...
Access flow 500-1000 mL/min with >20% reduction from baseline ^c	%	%	...
With clinical indicators of flow dysfunction ^d	%	%	...
Without clinical indicators of flow dysfunction ^d	%	%	...

Data are presented as proportions. The sum of the proportions may not add up to 100% because patients may have more than one clinical indicator of flow dysfunction.

^a Monitoring reports were not transferred to the research database in two study sites (OLVG and MUMC+ from 11-2024 onwards) because of technical issues with the electronic patient files.

^b Access flow is considered <500 mL/min only when the initial low flow measurement was confirmed in a subsequent dialysis session.

^c Baseline is the first flow measurement after randomization.

[figure not shown]
^d Clinical indicators of flow dysfunction refer to the decision rules for interventions defined in the study protocol (used to send notifications to the study sites).

When counting flow measurements, only measurements for surveillance and confirmatory measurements after low flow are counted. Flow measurements to evaluate interventions or as random repeats are excluded from analysis.

[figure not shown]
Statistical analysis: Chi squared tests.

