	Cannulation difficulties ^a		Cannulation failure ^b		Hematoma	
	OR (95% CI)	P	OR (95% CI)	P	OR (95% CI)	P
Sex (male)	... (....) (....) (....)	...
Age (/year)	... (....) (....) (....)	...
Body mass index (/kg/m ²)	... (....) (....) (....)	...
Use of antithrombotics						
No	Reference		Reference		Reference	
Antiplatelet therapy	... (....) (....) (....)	...
Anticoagulant therapy	... (....) (....) (....)	...
Dialysis treatments per week	... (....) (....) (....)	...
Vascular access type						
Arteriovenous fistula	Reference		Reference		Reference	
Radiocephalic fistula	Reference		Reference		Reference	
Brachiocephalic fistula	... (....) (....) (....)	...
Brachiobasilic fistula	... (....) (....) (....)	...
Arteriovenous graft	... (....) (....) (....)	...
Age vascular access (/month)	... (....) (....) (....)	...
Previous vascular access	... (....) (....) (....)	...
Previous vascular access interventions	... (....) (....) (....)	...
Baseline access flow (/100 mL/min)	... (....) (....) (....)	...
Cannulation technique						
Rope ladder	Reference		Reference		Reference	
Buttonhole	... (....) (....) (....)	...
Ultrasound-guided cannulation						
No	Reference		Reference		Reference	
Cannulation site determination	... (....) (....) (....)	...
Ultrasound-guided puncture	... (....) (....) (....)	...
Needle position assessment	... (....) (....) (....)	...
Needle type						
Steel	Reference		Reference		Reference	
Plastic	... (....) (....) (....)	...
Needle size						
15G	Reference		Reference		Reference	
16G	... (....) (....) (....)	...
17G	... (....) (....) (....)	...
Other	... (....) (....) (....)	...
Single needle prescription	... (....) (....) (....)	...

^a> 1 attempt to place and secure two needles (or one needle for dialysis sessions with single needle prescription)

^binability to place and secure two needles (or one needle for dialysis sessions with single needle prescription)

Statistical analysis: all variables will be entered into multivariable logistic regression models

Check for assumptions of statistical model: linearity, multicollinearity, and independence of errors

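### Tables 2G, 2H, 9A and 9B treat repeated reports, flow measurements and dialysis sessions from the same patients as independent

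*SAP*

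**What the plan says.** - **Table 9A** (cannulation practice by study group) has columns headed by numbers of sessions, for example "All patients (... dialysis sessions". It has a P column, and its only stated method is "Statistical analysis: Chi square tests".
- **Tables 2G and 2H** use monitoring reports and flow measurements as denominators, the latter headed "Monitoring (... measurements". Both have a P column and the note "Statistical analysis: Chi squared tests".
- **Table 9B** (predictors of cannulation problems) lists covariates fixed for a patient, such as sex and access type, beside covariates that belong to a session, such as needle size and ultrasound guidance. Its note reads "Statistical analysis: all variables will be entered into multivariable logistic regression models", followed by "Check for assumptions of statistical model: linearity, multicollinearity, and independence of errors".
- **Section 2.7** sets the frequency: "Physical examination of the vascular access will be done at each dialysis session", with flow measured monthly. Section 2.4 says patients are seen three times a week.
- **Elsewhere the SAP does allow for dependence:** a participant random intercept for event rates (5.2.1, 5.2.2), clustered standard errors for patency (5.2.1), generalized estimating equations for patient-reported outcomes (5.3) and a mixed linear model in Table 5B.
- **Section 5.1.2, item 7**, defines cannulation difficulty and failure as numbers of sessions per patient-year.

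**The concern.** A Pearson chi-square test, and the standard errors of an ordinary logistic regression, assume independent records. Sessions from one patient share the same access, anatomy and needling habits, and usually the same unit. The effective sample size is therefore much smaller than the number of rows.

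Section 3.1 treats p below 0.05 as statistically significant unless the SAP says otherwise, and nothing marks these P columns as descriptive. With about 828 × 156 ≈ 129,000 sessions, small chance differences between groups of patients would be reported as effects of the follow-up strategy. In Table 9B, ordinary patient-to-patient variation would be reported as predictors of cannulation problems.

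A second mismatch concerns the outcome. Table 9A tests the percentage of sessions with difficulty or failure, whereas 5.1.2 defines a rate per patient-year.

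**Working it through.** **Inputs from the SAP.** 828 patient-years and 417 patients (2.3); three sessions a week (2.4); monthly flow (2.7); two-sided 5% level (3.1). As a check on the first input, (1.96 + 0.84)² × (1.77 + 1.52) / 0.25² ≈ 413.2 with unrounded normal quantiles. This is consistent with the stated 414 patient-years per arm, or 828 in total.

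**Assumed.** The ICC, which the SAP does not give, and the re-randomisation rate. Table 2L, Figure 2E and 5.2.1 show that patients can change arm, but no rate is stated. The values used are 1.77 per year (the intervention rate in 2.3) and 1.0 per year.

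**Records per patient.** 828 / 417 = 1.986 years. Sessions: 3 × 52 × 1.986 ≈ 310. Flow measurements: 12 × 1.986 ≈ 23.8.

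**Patients who stay in one arm.** The design effect is DEFF = 1 + (m − 1) × ICC, where m is the number of records per patient. The actual type I error of a nominal 5% test is 2Φ(−1.96 / √DEFF). For sessions at ICC 0.01, DEFF = 1 + 308.8 × 0.01 = 4.09, √4.09 = 2.02, and 2Φ(−0.97) = 0.33.

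**Patients who change arm.** Let patient i contribute m1i and m0i records to the two arms, whose totals are n1 and n0, and let wi = m1i/n1 − m0i/n0. Then DEFF = (1 − ICC) + ICC × Σwi² / (1/n1 + 1/n0). With no switching this reduces to the formula above. It was evaluated for 417 patients re-randomised 1:1 at a Poisson rate.

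| Records | ICC | One arm: DEFF, type I | 1.77 per year: DEFF, type I |
|---|---|---|---|
| Sessions | 0.01 | 4.09, 33% | 2.27, 19% |
| Sessions | 0.05 | 16.44, 63% | 7.31, 47% |
| Sessions | 0.10 | 31.88, 73% | 13.63, 60% |
| Flow | 0.01 | 1.23, 8% | 1.09, 6% |
| Flow | 0.10 | 3.28, 28% | 1.88, 15% |
| Flow | 0.30 | 7.85, 48% | 3.65, about 30% |

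At 1.0 re-randomisation per year the session figures are 24%, 53% and 65%.

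**Simulation check.** Beta-binomial data with no group effect and an assumed event probability of 5% (1,500 runs) gave, in the order of the table rows:
- sessions, one arm: 32%, 65%, 74%; re-randomised: 19%, 45%, 60%
- flow, one arm: 8%, 28%, 49%; re-randomised: 6%, 16%, 30%

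In a separate simulation of patients staying in one arm (2,000 runs, ICC 0.01 to 0.20), comparing patient-level proportions brought the type I error back to 4.7% to 5.6%.

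**Table 9B.** For a covariate that is constant within a patient, the correct standard error exceeds the naive one by √DEFF: √4.09 = 2.0 at ICC 0.01 and √31.88 = 5.6 at ICC 0.10. Re-randomisation gives no relief here, because sex or access type does not change with the arm. No single factor applies to covariates that vary between sessions; it depends on how much they vary within patients.

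**The case against.** **Size and direction depend on unknowns.** The SAP gives neither the ICC nor the re-randomisation rate. For flow at ICC 0.01 the error is only 6% to 8%. If every patient split follow-up exactly evenly between arms, DEFF would be 1 − ICC and the test would be conservative (3.9% at ICC 0.10, 1.9% at 0.30). That stands as a caution against reading the percentages as precise. It does not rescue the tests: random re-allocation does not produce even splits, and a conservative test is still not a 5% test. The rate of 1.77 counts all access interventions. Table 2L looks at re-randomisation only after clinical success and excludes abandonment, so the true rate is probably lower, which moves the result towards the one-arm figures.

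**Other inputs are approximate.** A footnote to Table 2H says monitoring reports from two sites were not transferred, so reports per patient in 2G will average fewer than 310. Figure 2E shows 375 patients rather than 417. The one-arm design effect depends on records per patient, not on the number of patients, so neither point changes the picture.

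**Table 9B.** Its unit is not stated outright. The session level is inferred from its covariates and its footnotes, which refer to sessions with a single-needle prescription. Independence is listed for checking, but repeated sessions breach it by design and no remedy is named.

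**These tables are not decisive.** True: 2G and 2H report study progress, and the item 7 outcomes are explanatory. This limits the consequence, not the error.

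**Other tables share the weakness.** Tables 2J, 2K and 3B also test repeated intervals or interventions without clustering, and 3C and 7A appear to. That is fair, and a reason to review those notes at the same time.

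**Conclusion.** The point holds. The SAP names methods that are wrong for the stated units of analysis, so this is not merely missing detail. For session-level comparisons the false-positive rate is far above 5% throughout the range examined: 19% to 73% for ICC 0.01 to 0.10, with or without re-randomisation at up to 1.77 per year. For monthly flow it runs from slight (6% to 8% at ICC 0.01) to large (about 30% to 48% at ICC 0.30). Intervals in 9B for patient-constant predictors are too narrow by a factor of about 2.0 to 5.6 at ICC 0.01 to 0.10. These figures assume one common ICC over follow-up and the same number of records per patient-year.

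The primary, complication and thrombosis models carry a participant random intercept and are not touched. The strongest part of the finding is Table 9B and the cannulation difficulty and failure rows of 9A. The change should be made before analysis.

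**What to change.** - **2G, 2H and the binary rows of 9A:** replace the chi-square tests with logistic GEE or mixed-effects logistic models clustered on patient, or with tests using patient-clustered robust variances.
- **Multi-category rows of 9A** (ultrasound guidance, needle size, arterial and venous punctures): use multinomial or ordinal versions, or a permutation or bootstrap test that resamples patients.
- **Purely descriptive practice rows:** dropping the p-value is enough and is the cheapest option.
- **9B:** state that the unit is the session, and fit a patient random intercept, GEE or cluster-robust standard errors.
- **Cannulation difficulty and failure:** analyse as counts per patient-year with a participant random intercept and log time as offset. State a log link explicitly so that the exponentiated coefficient is a rate ratio, because 5.2 names an identity link.
- **Clarification only:** Figures 6E to 6G ask for confidence intervals for the area under the curve without naming a method. A bootstrap that resamples patients would suit.

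The cost is edits to the table notes and some standard R code, with no new data. The results will show wider, correct intervals and fewer small p-values.
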